Our study outcomes are all individual participant outcomes and randomized by sites to ensure we have enough Athelas devices to pass out. We will randomize the individuals by site (N = 60 sites, approximately 3-5 prescribers per site) randomized controlled effectiveness trial to assess if CHAMPION (150 prescribers) significantly increases clozapine prescribing, persistence, knowledge and self-reported competence compared to Enhanced Treatment as Usual (ETAU, N = 30 sites, 150 prescribers). We may have participants from more

CHAMPION PROTOCOL

than 60 sites and more than 300 enrollments to reach the target of 300 prescribers. In addition, individual prescribers signing up will also be randomized to the two conditions. .

We will assess provider level outcomes (knowledge and self-reported competence) immediately before and after the intervention (12 months) and patient level prescribing outcomes (from administrative data) for the year prior to the intervention, during the year of the intervention and for the year following the intervention. This will allow us to estimate the baseline level of clozapine prescribing, the impact during the intervention year and the sustainability of any effects during the year after the intervention is no longer active.

Randomization Procedures

Randomization will occur at the site level for enrolled sites and individual level for prescribers not at enrolled sites. There are NO site outcomes, this randomization allows for the devices to be given to providers in groups to ensure all groups can get a device. The randomization schedule will be created by the study statistician using a randomized block design (block = rural/urban/suburban). We will randomly assign each clinic/prescriber into one of the two study groups using a 1 (CHAMPION) to 1 (ETAU) assignment. Random assignment will occur after agency recruitment and prescriber baseline assessments are completed.

CHAMPION Intervention Condition

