The Hilltop institute maintains private and secure files and will be transferring requested data to the University of Maryland School of Medicine, Division of Services Research only through a secure file transfer protocol, Accellion. All data kept at the Division of Services Research are strictly confidential and secure.

CHAMPION PROTOCOL

Data Elements will include:

We will begin to collect data retrospectively for one year prior to the start of the CHAMPION intervention. This is slated to occur in approximately June of 2021 for the period of December of 2019 onward. We will collect data until one year after the CHAMPION ends or around June of 2023. Thus, we will be examining Medicaid data for a period of December 2019 to December of 2023 approximately.

The elements we will be collecting include collecting Maryland Medicaid recipient data for those who are over the age of 18. We are asking for data on those with a 295 diagnosis so we can examine antipsychotic and clozapine treatment. We anticipate approximately 350,000 antipsychotic prescriptions and 75,000 clozapine prescriptions annually.

We will have participant ID to link records for examining adherence and persistence. Thus, we will have Medicaid enrollment and demographic data, inpatient and outpatient claims data, other professional fee services, pharmacy data and provider information. The provider linkage is needed to link the knowledge and competence testing to rates of prescribing. Specifically, this includes:

Date of Service	Dates for prescription
Drug Name	Identification of antipsychotic name
Drug Formulation	Route of administration of type of antipsychotic
Strength	Dose of the Antipsychotic
Quantity	Number dispensed
Participant's Medicaid ID	Identification number of the patient
Claims data	Inpatient and Outpatient services for 295 diagnosis
Age	Age of patient
Zip code	Zip code where living
Race	Race
Prescriber ID	Prescriber identification number
Prescriber zip code	Zip code of where the prescriber resides
Prescriber county	County where the prescriber resides

HMIS Data and Security

CHAMPION PROTOCOL

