b. Persistence to clozapine: Incident episodes of clozapine prescriptions will be identified by a 90 day look back period to identify a new episode of care. Persistence will be measured as the duration of the clozapine episode (in days) from the date of the first prescription record until the first gap of more than 45 days between prescriptions. Prescribing gaps will be calculated by first adding the days' supply to the dispensing date of each prescription to identify the date the prescription should be exhausted. Days that the patient is hospitalized will not be included in the calculation of episode duration. The first gap in prescribing of 46 days or more will be considered a discontinuation of the medication. An episode will only be right censored at the study endpoint, otherwise an episode can continue into the next time period. If a person has more than 1 episode of clozapine use during any time period, we will select the first episode.

Specific Aim 2: We will measure two educational outcomes: self-reported competence of prescribers/clinical team in using clozapine and knowledge associated with clozapine treatment. These will both be measured before and after the 12-month intervention period. These outcomes have been selected, because they are measurable and pilot data has already established that prescribers/clinical team will rate competence and answer questions on clozapine knowledge. In addition, we will pilot-test all questions and review the self-reported competence measure prior to the administration of the CHAMPION intervention.

a. Competence: Our measurement of competence will be based upon self-report assessment guided by Bandura's theory of self-efficacy (2, 3) and we are using a definition of competence as "the perceived self-efficacy rating of one's judgment to use clozapine"(2, 4). We will use a Visual Analog Scale (VAS) (0-100 mm) will serve as the primary outcome. Self-reported competence ratings will be evaluated for the overall use of clozapine and for each of the CHAMPION session topic areas. The VAS format has been found to be superior

CHAMPION PROTOCOL

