To control for Type I errors, we will use the sequential Bonferroni-type procedure for dependent hypothesis tests of Benjamini and Hochberg (16) to control the false discovery rate at 5%. The false discovery rate is the expected (or on average) proportion of falsely rejected hypotheses. This procedure will be applied to the family of tests on the multiple associated measures corresponding to each aim. We will also control for if randomized to site or individual.

Analyses for Each Specific Aim and Hypothesis

Specific Aim 1: To determine the effect of 12 months of exposure to CHAMPION on the clozapine prescribing practices of prescriber participants and the objectively measured medication persistence of the patients prescribed clozapine.

Specific Aim 1, Hypothesis 1: *Relative to the prescribers/clinical team randomized to the ETAU condition (POC and consultation), prescribers/clinical team randomized to CHAMPION will significantly increase the proportion of patients in their care who are prescribed clozapine, as assessed using Maryland Medicaid prescription data.* Clozapine prescribing will be measured as the proportion of patients with any clozapine prescriptions (See Approach 5a). We will use a mixed-effects, 2-level model generalized linear mixed model (SAS Proc GLIMIX, log link) with percent adherence as the dependent variable and treatment group (CHAMPION/ETAU), time (pre-CHAMPION year (t=1), CHAMPION year (t=2), follow-up CHAMPION year (t=3), and time by treatment group as the independent variables of interest. However, since the main outcome will be calculated at t=3, a contrast statement, within the context of the full model, will be used to compare the two treatment conditions at t = 3, controlling for baseline, to test the primary hypothesis with a random site effect to account for intra-site correlation (ICC). The test of hypothesis 1 will operationally be the test of whether the coefficient of the CHAMPION/ETAU condition term is significantly >0 (two-sided test) at time t = 3. Post hoc analyses will use the same model to test effects at t = 2.

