Specific Aim 1, Hypothesis 2: *For patients who are prescribed clozapine, the patients of prescribers/clinical team randomized to CHAMPION will exhibit significantly greater persistence to clozapine treatment compared to patients of prescribers/clinical team randomized to the ETAU condition, as assessed using Maryland Medicaid prescription data.* Persistence (Approach Section 5b) will be measured as number of days of clozapine use. An episode will be identified as having begun during the 1 year prior to CHAMPION, during CHAMPION, or in the year after CHAMPION ends. A person can only have one episode in each of the time periods. We will use a generalized linear mixed-effects, 3-level model (SAS Proc GLIMIX, Poisson link), with a random site and a random prescriber effect to account for within site and within prescriber correlation (ICC). The longitudinal portion of the model will be treated as described for hypothesis 1. The test of hypothesis 2 will

CHAMPION PROTOCOL

operationally be the test of whether the coefficient of the CHAMPION/ETAU condition term is significantly greater than zero (two-sided test) at time 3. Post hoc analyses will use the same model to test for effects at time 2.

Specific Aim 2: To determine the effect of 12 months of exposure to the CHAMPION intervention on the knowledge and self-reported competence of prescribers/clinical team prescribing clozapine and how those mechanisms of change are associated with increased clozapine prescribing and persistence.

Specific Aim 2, Hypothesis 3: *Relative to the prescribers/clinical team randomized to the ETAU condition, prescribers/clinical team randomized to CHAMPION will demonstrate significantly increased levels of knowledge (correct number of MCQs) and self-reported competence (mean score on 0-100 mm VAS).*

Knowledge and competence are continuous measures that can be assumed to be normally distributed.

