However, the indirect benefits to patients with serious mental illness and psychotic disorders in the State of Maryland are more considerable, as we believe that this study will increase prescriber self-reported competence and use of this superior antipsychotic medication. Patients may receive clozapine trials or be maintained more successfully than in the past. This could improve outcomes and may decrease hospitalizations and emergency room visits. It may lead to better job productivity and a host of other possible outcomes known to be associated with the path to remission and recovery. Also, unnecessary treatments with non-evidence-based treatments and long wait times for care could all be improved.

While financial compensation will be provided for the time and effort that participants provide and a stipend to the sites to organize snacks at the time of the CHAMPION, this is not considered a benefit of study participation.

Importance of the Knowledge to Be Gained

The risks that this study poses to participants are reasonable in relation to the anticipated benefits and potential heuristic value of the research. This study has the potential to improve clozapine prescribing, improve lives of many patients and decrease overall health system costs. We will learn if an ECHO intervention, CHAMPION, is effective for improving clozapine prescribing and we will understand if this effect can be mediated by prescriber self-reported competence scores. Given the importance of the information to be gained and the low risks, we feel this project has a high importance on knowledge to be gained.

We believe the risks of this study are far outweighed by the potential benefits to the participants and their patients with schizophrenia and that this will demonstrate an effective and sustainable way to improve the treatment of these patients

Data and Safety Monitoring Plan

CHAMPION PROTOCOL

This study puts forth a randomized double-blind trial where prescribers/clinical team of antipsychotic medications will be the enrolled population. The study is an educational intervention and no biophysiological intervention will be performed; being a minimal risk study. No Data Safety Monitoring Board (DSMB) is required but the PI and team will monitor this study as described below.

Roles and Responsibilities

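### Clozapine episodes that start in the pre-CHAMPION year keep accruing days after the intervention starts, so any baseline adjustment of the Hypothesis 2 comparison at t=3 would use a baseline that the intervention can change

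*Combined protocol and SAP*

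**What the plan says.** Under Primary Outcomes (b, Persistence to clozapine), the outcome is episode length in days, up to the first gap of 46 days or more. On censoring the section says: "An episode will only be right censored at the study endpoint, otherwise an episode can continue into the next time period".

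Under Specific Aim 1, Hypothesis 2, the start date decides the period: "An episode will be identified as having begun during the 1 year prior to CHAMPION, during CHAMPION, or in the year after CHAMPION ends". The model is a generalized linear mixed model with a Poisson link and random site and prescriber effects. For time it says: "The longitudinal portion of the model will be treated as described for hypothesis 1". The test is to "operationally be the test of whether the coefficient of the CHAMPION/ETAU condition term is significantly greater than zero (two-sided test) at time 3".

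The Hypothesis 1 text codes the pre-CHAMPION year as t=1 and adds that a contrast "will be used to compare the two treatment conditions at t = 3, controlling for baseline".

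Randomization Procedures places allocation after the baseline work: "Random assignment will occur after agency recruitment and prescriber baseline assessments are completed". Under Potential Benefits, the plan allows that patients already on clozapine may respond: "Patients may receive clozapine trials or be maintained more successfully than in the past".

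The study endpoint has no single date:
- The ETAU section has the observation period ending in August 2023.
- The HMIS section ends the post-intervention period on July 31, 2023.
- Data Elements gives about June 2023 and then says: "Thus, we will be examining Medicaid data for a period of December 2019 to December of 2023 approximately".

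**The concern.** A baseline should hold only what happened before treatment could act. Here a t=1 episode is a baseline record by its start date, yet its length can be set by what happens in the intervention year and the year after. Nothing in the plan stops the count when the intervention starts. If the intervention helps ongoing patients stay on clozapine, the CHAMPION arm's baseline rises, and adjusting for it subtracts part of the effect. More patients do not remove such a bias. Hypothesis 2 is one of the two Aim 1 hypotheses, and persistence is also an outcome in the Hypothesis 4 mediation analysis.

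A second, separate gap lies in the same place. The outcome definition describes right censoring, but the Poisson model of days names no way to handle it. Potential follow-up falls from about 2-3 years for t=1 starters to 0-1 year for t=3 starters.

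**Working it through.** **The plan's own figure.** Power for Hypothesis 2 is given as above 95% at d = .3 and ICC .20. The number of clozapine patients per prescriber, m, is not stated. With 85% of 300 = 255 prescribers, effective n per arm = 127.5m/(1 + 0.20(m − 1)). For m = 4 this is 510/1.6 = 318.75, and power is 0.966; for m = 3 it is 0.939. The figure is attainable, but it says nothing about baseline adjustment, so it neither supports nor answers the concern.

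**Assumptions, not in the documents.** Constant discontinuation hazard with mean μ = 200 [400] days; uniform start dates; intervention start at day 365 and end at day 730; endpoint at day 1095. The CHAMPION hazard ratio (HR) is 0.75 and also acts on ongoing episodes. It applies either from day 365 (immediate) or falls linearly to 0.75 by day 730 (gradual). Square brackets are for μ = 400.

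**1. Share of t=1 days after intervention start (ETAU).**
- Let s = (μ/365)(1 − e^(−365/μ)), the share of t=1 starters still on clozapine at day 365: 0.460 [0.656].
- Mean days before day 365 = μ(1 − s) = 108.1 [137.7]. The t=3 window gives the same mean.
- Mean t=1 days as written = μ(1 − s·e^(−730/μ)) = 197.6 [357.7].
- Share after the start = 1 − 108.1/197.6 = 45% [1 − 137.7/357.7 = 62%].

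At one-year persistence of 40-80%, the share is 61-76%.

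**2. Full t=3-minus-t=1 contrast.** Share of the log effect lost = ln(t=1 ratio)/ln(t=3 ratio). Without contamination the t=1 ratio would be 1.00. The rate ratio is discontinuations per person-day, CHAMPION over ETAU; it handles the censoring.

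| Measure, onset | t=1 ratio | t=3 ratio | Full contrast | Log effect lost |
|---|---|---|---|---|
| Rate, gradual | 0.942 [0.902] | 0.750 | 0.797 [0.832] | 21% [36%] |
| Rate, immediate | 0.871 [0.836] | 0.750 | 0.861 [0.897] | 48% [62%] |
| Mean days, gradual | 1.0494 [1.0554] | 1.1234 [1.0688] | 1.070 [1.013] | 41% [81%] |
| Mean days, immediate | 1.127 [1.114] | 1.123 [1.069] | 0.997 [0.96] | about 100% [over 100%] |

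Example, first row: ln 0.942/ln 0.750 = 0.060/0.288 = 21%. The mean-days rows also carry the unequal windows and the days counted as complete, so they overstate what the baseline alone does.

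**3. Baseline as covariate.** The slope is the reliability of a prescriber mean at ICC .20: 0.20 for one episode, and 4 × 0.2/(1 + 3 × 0.2) = 0.50 for four. If prescriber effects are stable on the hazard, log days respond with elasticity 0.95 at t=1 and 0.45 at t=3 [0.74 and 0.26], so the slope is scaled by about 0.47 [0.35]. Loss = slope × scale × mean-days loss.
- Gradual: 0.2 × 0.47 × 0.41 = 4%, up to 0.5 × 0.47 × 0.41 = 10% [6-14%].
- Immediate: 10-24% [11-29%].

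**4. Other assumptions (mean days, full contrast, gradual onset).** The reference is 41% [81%].
- HR 0.6 to 0.9: 39-44% [79-84%].
- Falling hazard, Weibull shape 0.7: 33% [46%]; shape 0.5: 23% [28%].
- Half the log-HR in ongoing patients: 21% [42%].
- Endpoint 31 December 2023: 1 − ln 1.113/ln 1.176 = 34% [1 − ln 1.029/ln 1.101 = 70%].
- No effect on ongoing patients: no loss.

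**5. After a cut at day 365.** The t=1 ratio is 1.00 in expectation and the full-contrast rate ratio returns to 0.750. A censoring-aware model without the cut leaves it at 0.797 [0.832] under gradual onset.

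**The case against.** The strongest reply is that Hypothesis 2 states its own test, the condition term at time 3, and that control for baseline is Hypothesis 1 wording brought in by a general cross-reference. This stands in part. Read as a simple t=3 contrast, the test has no such bias. But the cross-reference is explicit, and a simple contrast would drop an adjustment that the borrowed model describes. The plan leaves the choice open.

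It is also fair that the size is assumed. A falling hazard or a weaker effect in ongoing patients reduces the loss, and about half or more of the gradual-onset loss in mean days comes from the unequal windows and unhandled censoring. Letting episodes run on is sensible for t=2 and t=3; only a baseline needs the cut. Finally, the Primary Outcomes section leads with the prescribing proportion and adds persistence to it.

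A reader might infer that the plan will cancel or reverse a real effect, since the immediate-onset contrast in days is 1.00 [0.96]. The documents do not support that: they fix neither the contrast nor any persistence rate, hazard ratio or speed of onset, and that figure mixes two defects. Nor is a false positive implied. With no effect, this rule leaves both arm ratios at 1.00.

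**Conclusion.** The persistence baseline is wrong as written: t=1 episodes include post-randomization days, and nothing in the plan corrects this. The harm is conditional. It needs an adjustment for t=1 and a response among patients already on clozapine, and it then pulls the t=3 effect towards no effect. On the assumptions above, with HR 0.75, a full contrast with censoring handled loses 21% [36%] of the log effect under gradual onset and 48% [62%] under immediate onset. Covariate adjustment loses 4-10% [6-14%] and 10-24% [11-29%]. A simple t=3 contrast loses nothing. The existence of the problem rests on the text alone; its size rests on assumptions that the documents neither give nor exclude. Unequal follow-up does not by itself bias the comparison of arms within a period, but mean days cannot be compared across periods, and the model should handle the censoring. This should be fixed before analysis.

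**What to change.** 1. State the Hypothesis 2 contrast at t=3: simple difference, t=1 as covariate, or t=3 minus t=1. This comes first, because a simple contrast removes the problem on its own.
2. If t=1 is adjusted for in any form, censor episodes that start in the pre-CHAMPION year on the day the intervention starts. Report their later days descriptively.
3. Replace the Poisson model of days with one that accepts right censoring, such as time to discontinuation with site and prescriber random effects. This also handles the unequal windows, so t=2 episodes need no cut.
4. Give one study endpoint date, reconciling the ETAU, HMIS and Data Elements sections.

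The cost is a few sentences, a date cut in administrative data and a re-specified model. With the cut, observed ETAU t=1 discontinuations fall from 98.8% to 54.0% of episodes [89.4% to 34.4%]. Assuming equal episode numbers per period and no clustering, the standard error of a full contrast rises by a factor of √((1/0.540 + 1/0.540)/(1/0.988 + 1/0.540)) = 1.14 [1.20], that is by about 14% [20%]. A simple t=3 contrast needs no cut and pays nothing.

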Analysis of Secondary and Exploratory aims.														
Archive ECHO lectures for website at end of 12 months														
Period of Medicaid Data Collection 2 (Aim 1)														
Post Testing on Knowledge and Self-Reported Competence (Aim 2)														
Meetings with NASHMPD														
Analysis of Project ECHO Post data														
Make videotaped ECHOs available to all participants once 12-month Medicaid data completed.														
National Webinar with NASHMPD and APA CSS SMI														
Submit symposium abstract to national														

CHAMPION PROTOCOL

meetings, e.g. IPS, SIRS														
Data Repository Submission														

STATISTICAL DESIGN AND POWER

Primary Outcomes

Specific Aim 1: The primary outcome examines Maryland Medicaid (and HMIS for inpatient) prescription data, which will be used to assess the increase in the proportion of patients treated with clozapine for those in the care of prescribers/clinical team randomized to the CHAMPION relative to the ETAU condition. We will also examine persistence in the use of clozapine for patients who are prescribed clozapine under the care of prescribers/clinical team randomized to CHAMPION compared to prescribers/clinical team randomized to the ETAU. The specific outcome assessments using Medicaid data include:

a. Proportion of clozapine prescriptions: Clozapine prescribing rates will be calculated from Medicaid prescription data. National Prescriber Identification (NPI) numbers will be used to identify the antipsychotic prescription records for each prescriber in the study. The denominator will be the number of unique individuals with a diagnosis of schizophrenia who had at least 1 prescription for an antipsychotic during each time period (12 months prior to start of study, during active study participation, and 12 months after the intervention period ends). For each individual in the sample, an indicator will be created that reflects whether the person had any prescription for clozapine during each of the time periods.

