Hypothesis 3: Although the variables for hypothesis 3 are normally distributed, the specifications are the same and the power calculations are identical to those noted above. Based on literature described in Approach section 10 above, we anticipate changes in knowledge and competence to be large ($>.8$).

Hypothesis 4: Using the values above and the SAS macro from O'Rourke and MacKinnon (14), the power to detect indirect effects (mediation) will be greater than .80 when using the bias corrected bootstrap procedure when paths a and b are at least 0.3 (small to medium effects anticipated).

Statistical Analyses Overview

All data will be screened for errors using frequency and contingency tables and univariate and bivariate plots before formal analysis. These informal plots and summaries will allow us to be cognizant of data distribution characteristics before building regression models. We anticipate that our dependent variables will either have a distribution that is relatively bell-shaped or can be transformed to be relatively bell-shaped. Site will be included in all models as a random effect. Prescriber is nested within intervention arm, by design, and will be specified as a random effect in all analyses that include patient level data. The intercept will be designated as random to account for the non-independence across time point when appropriate. SAS PROC MIXED or GLIMIX will be used for the analyses described below (15).

CHAMPION PROTOCOL

Missing Data

All analyses will be conducted within an ITT framework. As described above, missing data for hypotheses 1 and 2 will be limited due to the use of Medicaid prescription records for those outcomes. For hypotheses 3 and 4, we will compare the baseline characteristics of the prescribers/clinical team who drop out prior to completing the 12-month assessment to those prescribers/clinical team who do complete the assessment. If necessary, we will investigate how estimates/results change over a range of several plausible assumptions regarding the missing mechanism together with multiple imputations to most accurately capture existent random variability.

Multiple Comparisons

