Transformations will be used if necessary. They will be measured at two time points (baseline and end of the 1-year CHAMPION). A General Linear Mixed Model (Proc MIXED) will be used to estimate the effects of the two groups on change in knowledge and competence with site as a random effect. The test of hypothesis 3 will operationally be the test of whether the coefficient of the CHAMPION/ETAU condition term is significantly greater than zero (two-sided test) at the post CHAMPION time point controlling for baseline. In exploratory analyses, we will examine individual competence scores related to outcomes as above while controlling for multiple comparisons.

Specific Aim 2, Hypothesis 4: *Prescriber self-reported competence will mediate the effect of the CHAMPION on clozapine prescribing and persistence.* A separate model will be used for each outcome. The independent variable will be group assignment, the dependent variable will be rate of clozapine prescribing during the year following CHAMPION and the persistence of clozapine episodes, and the mediator will be the overall self-reported competence score (0-100 mm VAS) measured at 12 months, controlling for baseline. We will use the product of coefficients approach to test mediation. The rationale behind this method is that mediation depends on the extent to which the independent variable changes the mediator (i.e., path a), and the extent to which the mediator affects the outcome variable (i.e., path b). The PROCESS (17) macro for SAS will be used to generate 95% bias corrected confidence intervals for the relative indirect effects and other parameters.

Exploratory Analyses

We will examine the role of race in moderating the effects of CHAMPION. To determine whether there was differential benefit of the program for the AA patients, race and interaction terms (time by race) will be added to the models described above. Despite our previous work, it is possible that increases in prescribing will not occur similarly between AA and Caucasian patients, however, we will use data collected to adapt future iterations of the topics related to AA if we do not see similar improvements in prescribing. Specifically, we will examine the two competence questions related to AA and ascertain the relationship of these specific measures to prescribing for AA and Caucasian patients. We will also look at other variables by site and patient that may contribute to outcomes and will analyze the other clinicians and examine.

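### The Hypothesis 1 primary model names an undefined dependent variable, leaves the unit of analysis inconsistent, and does not settle how the baseline year enters the test

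*Combined protocol and SAP*

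**What the plan says.** Four parts of the document bear on the primary analysis.

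- **Outcome.** Primary Outcomes, item a, counts unique patients with schizophrenia who had at least one antipsychotic prescription in a period. For each of them "an indicator will be created that reflects whether the person had any prescription for clozapine during each of the time periods". The Hypothesis 1 paragraph agrees: "Clozapine prescribing will be measured as the proportion of patients with any clozapine prescriptions". Hypothesis 4 uses the same quantity: "the dependent variable will be rate of clozapine prescribing during the year following CHAMPION".
- **Model.** The next sentence of the Hypothesis 1 paragraph specifies a "2-level model generalized linear mixed model (SAS Proc GLIMIX, log link) with percent adherence as the dependent variable". Its fixed terms are treatment group, time (t = 1, 2, 3) and their interaction. The only random effect it names is for site.
- **General rules.** Overview of the Study Design speaks of "patient level prescribing outcomes (from administrative data) for the year prior to the intervention" and the two later years. Statistical Analyses Overview says: "Prescriber is nested within intervention arm, by design, and will be specified as a random effect in all analyses that include patient level data". It adds that the intercept will be random, where appropriate, to allow for dependence between time points. Hypothesis 2 has a "3-level model (SAS Proc GLIMIX, Poisson link), with a random site and a random prescriber effect".
- **Test.** The primary comparison is a contrast at t = 3 within the full model, described as adjusted for baseline. The paragraph then defines the test as whether the condition coefficient at t = 3 differs from zero, two-sided.

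**The concern.** This is the primary analysis, and two analysts following the text could fit different models. They would probably agree on the outcome, because the surrounding text gives it, but the model sentence itself names another variable. They could differ on whether the record is a patient or a prescriber, on whether a prescriber term is included, and on whether t = 1 is subtracted, conditioned on or left out of the test.

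The ambiguity spreads. Hypothesis 2 takes its longitudinal part from Hypothesis 1, and the exploratory race analyses add terms to the same models. Recruitment and the intervention are complete according to the HMIS section, so any choice still open could be made with outcome data in hand.

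**Working it through.** **1. Dependent variable.** The outcome definition, the sentence before the model and Hypothesis 4 all describe clozapine prescribing. Percent adherence has no definition in the document. It is not the Hypothesis 2 outcome either, which is the duration of a clozapine episode in days.

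**2. Unit of analysis: the two readings side by side.**

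| Source | Points to |
|---|---|
| Overview of the Study Design | patient level |
| Primary Outcomes, item a | patient level (yes/no per patient) |
| Hypothesis 1 model: two levels, site effect only | one proportion per prescriber |
| Power, Hypothesis 1 | one proportion per prescriber |

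The power calculation can be approximately reproduced using prescriber-level inputs alone.
- Inputs: 4% v 15%, h = 0.39, alpha 0.05, power 0.80, ICC 0.01 for prescribers within site, 4–5 per site.
- Effect size: h = 2·asin(√0.15) − 2·asin(√0.04) = 0.393.
- Per arm: 2(1.960 + 0.842)²/0.39² = 103.2.
- With 5 per site: 103.2 × (1 + 4 × 0.01) = 107.3, so 108 per arm and 216 in all. 216/0.85 = 254.
- With 4 per site: 103.2 × 1.03 = 106.3, so 214 in all. 214/0.85 = 252.

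The match to 254 assumes that it already allows for 85% of prescribers having records, which the text does not say. (300 × 0.85 = 255 would suggest that 254 is the number needed with data.) On either view, no number of patients per prescriber enters.

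On the patient-level reading, the general rule demands a prescriber random effect. On the prescriber-level reading that rule is not triggered, but each prescriber gives up to three yearly values, which are correlated. That also needs a prescriber-level term, and the only provision for it is the random intercept to be used where appropriate.

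**3. Baseline.** t = 1 is a level of the time factor, so it is a response. The contrast is said to adjust for it, but the test sentence subtracts nothing. No baseline covariate is listed among the model terms. The text therefore leaves a comparison at t = 3 alone, a t = 3 minus t = 1 contrast, or some other use of t = 1.

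**4. Illustration of what the baseline choice can do.** This is not an estimate for the trial. Assumptions: normal approximation; 80% power for the test at t = 3 alone; correlation r between t = 1 and t = 3; k = variance of the arm difference at t = 1 divided by that at t = 3. Neither r nor k is in the documents. Two values of k follow from the planned rates if 4% is assumed in both arms at t = 1:
- raw scale: k = (2 × 0.04 × 0.96)/(0.04 × 0.96 + 0.15 × 0.85) = 0.0768/0.1659 = 0.46;
- log scale: k = (2 × 0.96/0.04)/(0.96/0.04 + 0.85/0.15) = 48/29.67 = 1.62.

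Power of the change contrast = Φ(2.80/√(1 + k − 2r√k) − 1.96). Power with t = 1 as a response and a common baseline mean (in large samples, the same as a covariate) = Φ(2.80/√(1 − r²) − 1.96), which does not depend on k.

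| | r = 0.3 | r = 0.5 | r = 0.7 |
|---|---|---|---|
| t = 3 alone | 80% | 80% | 80% |
| Change, k = 0.46 | 78% | 89% | 98% |
| Change, k = 1 | 66% | 80% | 95% |
| Change, k = 1.62 | 54% | 68% | 87% |
| Common baseline mean | 84% | 90% | 98% |

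Within this approximation all three hold the 5% error rate. The change contrast can have more or less power than the comparison at t = 3 alone.

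**5. Type I error without the prescriber term.** A simulation assumed 30 sites per arm, 5 prescribers per site, 10 patients each, balanced data, a continuous outcome at one time point and site ICC 0.01. A site effect estimated from the data gave rejection rates of 0.049, 0.050 and 0.050 at prescriber ICCs of 0, 0.05 and 0.20. The site term absorbs the prescriber variation.

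**The case against.** The best defence is that the plan can be read coherently. Percent adherence is a slip that the preceding sentence corrects. Hypothesis 1 has prescribers within sites (two levels), while Hypothesis 2 has patients within prescribers within sites (three levels). The power section uses the ICC that matches each. General rules in the overview need not be repeated in every paragraph, and the random intercept could supply the prescriber term.

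Much of this stands. A reader might infer that the model plainly omits a random effect that the plan requires. The documents do not support that, because the requirement applies only to patient-level data and the power section supports one proportion per prescriber. What remains is that the plan never says which unit it uses, and its design and outcome sections point the other way. Where appropriate is also not a specification for a primary model.

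A reader might also infer a fixed loss of power, or a fixed rate of conflicting verdicts, from comparing a baseline covariate with a change contrast. That is not supported either: the paragraph lists no covariate, and the figures move widely with two quantities that the documents do not give. Nor does the plan imply losing prescribers who lack t = 1 data, since t = 1 is a response.

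**Conclusion.** The point holds as a defect of specification in the primary analysis, and it should be corrected.

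- The dependent variable in the model sentence is wrong. This rests on the text alone.
- The unit of analysis is inconsistent. On either reading a prescriber-level term is needed for the repeated years, and the plan leaves it optional.
- The contrast and the test sentence do not agree on whether or how t = 1 is used.

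No single size can be given. Under the stated assumptions the change contrast has 54% to 98% power where the comparison at t = 3 alone has 80%. This shows only that the choice matters. A reader might infer an inflated error rate from the missing prescriber term. The simulation gives no support for that in a balanced design, and none is claimed. The planned 254 is not disputed.

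**What to change.** Rewrite the Hypothesis 1 model paragraph as follows.

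1. Replace percent adherence with the number of patients with any clozapine prescription out of eligible patients, per prescriber per period, modelled as binomial.
2. Include random effects for site and for prescriber within site, treating each unaffiliated prescriber as its own cluster.
3. Keep t = 1 as a response with a common mean across arms. This retains prescribers without t = 1 data.
4. Define the primary test, in one sentence, as the condition effect at t = 3 from that model.
5. Add the rural/urban/suburban randomisation block as a fixed effect, beside the planned term for site or individual randomisation. Its absence contradicts nothing; adding it is a free improvement.

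The paragraph should also say whether prescriber-by-period variation and the same patients recurring across years are modelled, since a prescriber intercept alone does not cover them.

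The cost is SAP wording, model code and a slightly more complex fit. A fallback should be stated in advance if the log link does not converge: logit link, same fixed and random effects. The fallback changes the effect measure from a risk ratio to an odds ratio. At the planned rates, ignoring the random effects, these are 0.15/0.04 = 3.75 and (0.15/0.85)/(0.04/0.96) = 4.24. No new data are needed and the sample size does not change. The amendment should be dated before prescribing is compared by arm.
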